10.0 Statistical Design

This is a single-arm, phase II study of combination of lenalidomide and ofatumumab. The study population consists of patients with previously treated CLL/SLL and patients will have to have received at least one purine analog-based regimen. The primary outcome is overall response. A Simon's two-stage minmax design will be used for this study. A sample size of 36 is chosen to differentiate between a good response rate of 40% and a poor response rate of 20% with 90% power at a significance level of 0.1. In particular, 19 patients will be enrolled at the first stage. If there are 3 or fewer responses in the first 19 patients, accrual will be suspended until we have 4 responders among the first 19 patients. The trial will be terminated if all 19 patients have been evaluated for 6 cycles and there are 3 or fewer responses; otherwise another 17 patients will be treated for a total of 36 patients. If there are 10 or fewer responses among 36 patients, the treatment will be concluded ineffective. The probability of early termination due to futility is 0.46. Overall response includes complete remission (CR) and partial remission (PR). Patients are considered non-responders if there is progression of disease. CR, PR and SD allow continuation of treatment.

The probability of toxicity (grade 3 and 4 non-hematological) will be monitored based on the Bayesian model (beta-binomial) by assuming a priori probability of toxicity following Beta (1,1). The trial will be terminated if $\text{Prob}(\text{toxicity} > 0.33 \mid \text{data}) > .85$. Following this rule, the trial will be terminated if $[\# \text{ toxicities}]/[\# \text{ patients evaluated}] \geq 3/5, 5/10, 7/15, 9/20, 11/25, 13/30, \text{ and } 15/35$. A simulation study was performed to show the operating characteristics for the stopping rule based on 10,000 repetitions. The results are summarized in the

following table. For example, the trial will be terminated early 90.8% of times if the true toxicity rate is 50%.

True Prob(tox)	Pr(stop)	Median #Pts (25%, 75%)
0.10	0.011	36 (36, 36)
0.20	0.084	36 (36, 36)
0.30	0.305	36 (15, 36)
0.40	0.646	15 (5, 36)
0.50	0.908	10 (5, 15)
0.60	0.991	5 (5, 10)

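### The stage 1 futility stop requires all 19 patients to be evaluated for 6 cycles, so one early leaver can keep it from triggering

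*Combined protocol and SAP*

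**What the plan says.** All the decision rules stand in Section 10.0, Statistical Design.

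- **Design.** "A Simon's two-stage minmax design will be used for this study", with response rates of 20% (poor) and 40% (good), "with 90% power at a significance level of 0.1". The probability of stopping early for futility is given as 0.46.
- **Stage 1.** "19 patients will be enrolled at the first stage". With 3 or fewer responses, accrual is held until a fourth responder appears in that cohort.
- **Stop.** "The trial will be terminated if all 19 patients have been evaluated for 6 cycles and there are 3 or fewer responses".
- **Go.** The same sentence sends every other case to stage 2: "otherwise another 17 patients will be treated for a total of 36 patients".
- **Final rule.** 10 or fewer responses in 36 means ineffective.
- **Endpoint.** Response is CR or PR. On the other side the section says "Patients are considered non-responders if there is progression of disease". CR, PR and SD permit further treatment.

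The section gives no analysis population and no replacement rule. It does not classify a patient who dies, withdraws, stops for toxicity or has no assessment.

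The assessment times also differ. Section 10.0 makes the end of cycle 6 the first efficacy time point, and Section 4.0 lists an evaluation after cycle 6. Section 8.0 lists assessments after cycles 3 and 7 but none after cycle 6, and the visits in Section 7.0 follow the same pattern.

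**The concern.** The stop has two conditions: at most 3 responses, and six cycles of evaluation in every one of the 19. A patient who goes off treatment in cycle 2 can never satisfy the second. This includes patients who progress early: Section 10.0 names them as non-responders, but progression is not among the states that allow treatment to continue.

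In that case the text gives two answers. The suspension sentence keeps accrual closed because there is no fourth responder. The clause after the semicolon says that whenever the stop condition is not met, the next 17 are treated. The rule is thus undetermined in the situation it was written to decide. Early leaving is foreseeable, since the lenalidomide dose-modification table in Section 4.0 itself requires discontinuation for several toxicities. An inactive regimen would also tend to produce more early progression, so the stop is most likely to be blocked when it is most needed.

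At stake is the only futility rule in the plan. A further risk is that the treatment of leavers is settled after their responses are known.

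**Working it through.** **Inputs from Section 10.0:** p0 = 0.20, p1 = 0.40; stop at 3 or fewer of 19; ineffective at 10 or fewer of 36.

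**Assumed input:** d, the chance that a patient leaves before completing cycle 6 without a response. The documents give no value; 5%, 10% and 20% are used.

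**1. The plan's own figures.** Early termination at p0 is P(X ≤ 3), X ~ Bin(19, 0.20):

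0.0144 + 0.0685 + 0.1540 + 0.2182 = 0.455 (stated as 0.46).

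The probability of declaring activity is the sum over x = 4 to 19 of P(X = x) × P(Bin(17, p) ≥ 11 − x). It is 0.086 at p = 0.20 (type I error) and 0.902 at p = 0.40 (power). An exhaustive search for the minimax design returns the same 3/19 and 10/36. Expected sample size at p0 is 19 + 17 × (1 − 0.455) = 28.3. The stated design is correct.

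**2. The stop read literally.** It triggers only if nobody among the 19 leaves and there are 3 or fewer responses. The overall response rate is held at 20% with leavers as non-responders, so the rate among those who stay is 0.20/(1 − d):

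P(stop) = (1 − d)^19 × P(Bin(19, 0.20/(1 − d)) ≤ 3)

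| d | P(no leaver among 19) | P(≤ 3 responses, given no leaver) | P(stop) |
|---|---|---|---|
| 0 | 1 | 0.455 | 0.455 |
| 5% | 0.377 | 0.410 | 0.155 |
| 10% | 0.135 | 0.363 | 0.049 |
| 20% | 0.014 | 0.263 | 0.004 |

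If leaving is instead independent of response, P(stop) is (1 − d)^19 × 0.455 = 0.172, 0.061 and 0.007. The conclusion is the same.

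**3. If the unmet condition leads to stage 2.** Expected sample size at p0 is 19 + 17 × (1 − P(stop)) = 33.4, 35.2 and 35.9 at d = 5%, 10% and 20%, against 28.3 as designed. With no stage 1 stop at all, P(Bin(36, p) ≥ 11) is 0.089 at p = 0.20 and 0.910 at p = 0.40, both within the design limits.

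**4. If leavers without response were replaced (hypothetical).** The apparent null rate becomes 0.20/(1 − d), which is 0.211 at d = 5% and 0.222 at d = 10%. Putting these into the formulas of step 1 gives type I error of 0.115 and 0.153, and early termination of 0.41 and 0.36.

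**5. With every treated patient counted and leavers as non-responders.** The count of CR plus PR is again binomial in 19 and 36, so step 1 applies unchanged: 0.455, 0.086 and 0.902.

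**The case against.** The best defence is that the rule counts responses, so anyone who is not a CR or PR is a failure in effect. A sensible team would take a patient who has left as evaluated. Section 10.0 speaks of patients enrolled and treated, which suggests fixed denominators, and the later mention of a response variable coded yes or no leaves no third category. That reading would make the stop work, but the text does not state it, and the six-cycle condition points the other way.

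Three stronger readings are tempting and are not supported.

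- *Stable disease has no place in the rule.* A reader might infer this from the progression sentence. However, both stages count CR plus PR. A patient with SD through cycle 6 fills one of the 19 places, adds nothing to the count and cannot block the stop. On SD the sentence is only loosely worded, since it says if and not only if.
- *Type I error is inflated.* This would need leavers to be replaced, which the documents neither provide for nor forbid. Silence is a gap, not permission. Early progressors are also named as non-responders, so they would not be candidates for replacement, and a replacement would not be one of the first 19. The figures in step 4 show only why the point should be closed.
- *The trial is stuck and can neither stop nor go on.* The suspension sentence does imply a hold, under which no further patients would be exposed. The clause on the next 17 implies continuation. The fault is the conflict between them.

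It is also fair to say that the chance of at least one leaver is not the chance of a failed stop, because a failed stop also needs 3 or fewer responses. The table in step 2 takes that into account.

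Appendix F, which Section 8.0 cites for the response criteria, was not among the material reviewed. It may contain a rule for unevaluable patients.

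**Conclusion.** The concern holds as a defect in the wording of the stage 1 stop. Read as written, a single patient who does not reach six cycles prevents termination, and two sentences then disagree on what follows. At a true response rate of 20%, the chance that the stop triggers falls from 0.455 to 0.155, 0.049 or 0.004 when 5%, 10% or 20% leave early without response. Those rates are assumptions, with patients taken as independent.

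What is lost is protection against treating further patients with an inactive regimen. Control of false positives is not lost: with all 36 treated, type I error stays below 0.1 and power above 90%. The design numbers themselves are right. The amendment should be made because it concerns the primary endpoint and costs little.

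**What to change.** Amend Section 10.0 to say that:

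1. all treated patients count in the fixed denominators of 19 and 36, and none is replaced;
2. any patient without a documented CR or PR by the stage 1 assessment is a non-responder, whether because of stable disease, progression, death, withdrawal, new therapy or a missing assessment, and the same classification applies in the final analysis of 36;
3. stage 1 is complete once each of the 19 has reached that assessment or left treatment, and the trial then stops if there are 3 or fewer responses.

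Reword the suspension sentence and the clause on the next 17 so that both follow from item 3: accrual is held while the outcome is open, and stage 2 opens only with at least 4 responses. Name the stage 1 assessment and reconcile its timing across Sections 4.0, 7.0, 8.0 and 10.0. Check Appendix F for any rule on unevaluable patients and bring it into line.

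The cost is a few sentences, with the sample size unchanged at 36. The observed response rate may be slightly lower than one based on evaluable patients only.

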The first time point to evaluate efficacy and toxicity will be at completion of cycle 6 of treatment. Toxicity will be monitored closely during the entire treatment, but toxicities occurring after cycle 6 will not be applied to the stopping boundaries. The descriptive statistical analysis can be used to explore the data, including histograms or box-plots, proportions, mean, standard deviations. The Fisher's exact test will be used for the univariate analysis on categorical variables (response variable with Yes versus No, for example). The t-test or Wilcoxon test will be used for continuous variables (Age and WBC, for example). Descriptive statistical analysis will also be used to report correlative studies and the quality of life questionnaire.

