11.0 Amendments, Deviations, Regulatory

Protocol Amendments

Any amendment to this protocol must be agreed to by the Principal Investigator and by M. D. Anderson Cancer Center and by Celgene and GSK. Amendments should only be submitted to IRB after consideration of M. D. Anderson Cancer Center, Celgene and GSK review. Written verification of IRB approval will be obtained before any amendment is implemented.

Protocol Deviations

When an emergency occurs that requires a deviation from the protocol for a subject, a deviation will be made only for that subject. A decision will be made as soon as possible to determine whether or not the subject (for whom the deviation from protocol was effected) is to continue in the study. The subject's medical records will completely describe the deviation from the protocol and state the reasons for such deviation. In addition, the Investigator will notify the IRB in writing of such deviation from protocol.

Investigator Responsibilities

Investigator responsibilities are set out in the ICH guideline for Good Clinical Practice (GCP) and in the US Code of Federal Regulations.

Investigators must enter study data into MDACC's PDMS. The Investigator will permit study-related monitoring visits and audits by MDACC's ORERM, Celgene or its representatives, IRB/EC review, and regulatory inspection(s) (e.g., FDA, EMEA, TPP), providing direct access to the facilities where the study took place, to source documents, to CRFs, and to all other study documents.

The Investigator, or a designated member of the Investigator's staff, must be available at some time during monitoring visits to review data and resolve any queries and to allow direct access to the subject's records (e.g., medical records, office charts, hospital charts, and study related charts) for source data verification. The data collection must be completed prior to each visit and be made available to MDACC ORERM and the Celgene representative so that the accuracy and completeness may be checked.

Institutional Review Board/Ethics Committee Approval

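### The printed Pr(stop) values at true toxicity rates of 40%, 50% and 60%, and the 90.8% example, are not those of the seven-look toxicity rule; they fit looks to 30 only

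*Combined protocol and SAP*

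**What the plan says.** Section 10.0 (Statistical Design) monitors grade 3 and 4 non-hematological toxicity with a beta-binomial model. The prior is Beta(1,1), and the trial stops when the posterior probability that the toxicity rate exceeds 0.33 is above 0.85. The section turns this into seven boundaries, reached when toxicities over patients evaluated are at or above 3/5, 5/10, 7/15, 9/20, 11/25, 13/30 or 15/35. The maximum sample size comes from the efficacy design: "otherwise another 17 patients will be treated for a total of 36 patients".

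On performance the section says: "A simulation study was performed to show the operating characteristics for the stopping rule based on 10,000 repetitions". The table that follows gives Pr(stop) of 0.011, 0.084, 0.305, 0.646, 0.908 and 0.991 at true rates of 10% to 60%, with the median and quartiles of the number of patients. The text then uses the 50% row as its worked example: "the trial will be terminated early 90.8% of times if the true toxicity rate is 50" percent. Nothing in the section says that any listed look was left out of the simulation.

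**The concern.** The rule is fully specified, so its stopping probabilities can be computed exactly and the simulated column should agree with them to within simulation error. In the three upper rows it does not.

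The table is the only place where the documents state how the safety rule performs, and the row chosen for the worked example is one of the three affected. The 50% rate also has a meaning of its own: Section 1.0 calls toxicity excessive when more than 50% of patients have a grade 3-4 non-hematological event. Someone who recomputes the table cannot tell whether the boundary list or the table describes the rule in force, and in particular whether 15/35 is operative.

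**Working it through.** **Inputs, all from Section 10.0.** Beta(1,1) prior; stop if P(rate > 0.33 | data) > 0.85; looks at 5, 10, 15, 20, 25, 30 and 35 evaluated patients; maximum 36 patients; 10,000 repetitions; the six printed Pr(stop) values.

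**Step 1: the boundaries.** With x toxicities in n patients the posterior is Beta(1 + x, 1 + n − x). The boundary is the smallest x whose posterior probability exceeds 0.85.

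| n | probability one below boundary | probability at boundary | boundary |
|---|---|---|---|
| 5 | 0.6870 | 0.9031 | 3 |
| 10 | 0.7193 | 0.8829 | 5 |
| 15 | 0.7469 | 0.8795 | 7 |
| 20 | 0.7704 | 0.8820 | 9 |
| 25 | 0.7907 | 0.8868 | 11 |
| 30 | 0.8085 | 0.8925 | 13 |
| 35 | 0.8242 | 0.8985 | 15 |

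All seven printed boundaries are reproduced, including 15/35.

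**Step 2: exact stopping probabilities.** Carry the binomial toxicity count forward patient by patient. At each look, remove the probability that lies at or above the boundary. The sum of what is removed is Pr(stop). At a true rate of 50%:

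- Look at 5: P(3 or more of 5) = (10 + 5 + 1)/32 = 0.5000.
- Look at 10: (1/32)(1/32) + (5/32)(6/32) + (10/32)(16/32) = 191/1024 = 0.1865.
- Looks at 15, 20, 25 and 30, same recursion: 0.0972, 0.0588, 0.0388, 0.0270.
- Sum to 30: 0.5000 + 0.1865 + 0.0972 + 0.0588 + 0.0388 + 0.0270 = 0.9083.
- Look at 35: 0.0196, so the seven-look total is 0.9083 + 0.0196 = 0.9279.

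The printed 0.908 is the sum to 30. The first-crossing probability at 35 is 0.0234 at a true rate of 40% (0.6465 + 0.0234 = 0.6699) and 0.0041 at 60% (0.9906 + 0.0041 = 0.9947).

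**Step 3: comparison with the table.** The Monte Carlo standard error (SE) is √[p(1 − p)/10,000], with p the exact value, and z = (printed − exact)/SE. At 50% with seven looks, SE = √(0.9279 × 0.0721/10,000) = 0.0026 and z = (0.908 − 0.9279)/SE = −7.7.

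| True rate | Printed | Seven looks | z | Looks to 30 | z |
|---|---|---|---|---|---|
| 10% | 0.011 | 0.0095 | 1.6 | 0.0095 | 1.6 |
| 20% | 0.084 | 0.0813 | 1.0 | 0.0811 | 1.1 |
| 30% | 0.305 | 0.3041 | 0.2 | 0.2978 | 1.6 |
| 40% | 0.646 | 0.6699 | −5.1 | 0.6465 | −0.1 |
| 50% | 0.908 | 0.9279 | −7.7 | 0.9083 | −0.1 |
| 60% | 0.991 | 0.9947 | −5.1 | 0.9906 | 0.4 |

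The sum of squared z over six rows is 114.3 for seven looks and 6.4 for looks to 30 (6 df; p about 3e-22 and 0.38). Rounding to three decimals moves a value by at most 0.0005 and cannot explain gaps of 0.0037 to 0.024.

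**Step 4: other explanations tried.** Each was tested against the same six rows.

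- Looks to 25 only: sum of squares 158.8 (0.881 at 50%).
- Strict inequality at the boundaries: 0.835 at 50%.
- An added look at 36: 0.938 at 50%.
- A look after every patient from the fifth: 0.952 at 50%.
- Dropping any look or shifting its boundary by one: looks to 30 fitted best; the next best had a sum of squares of 12.8.

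**Step 5: medians and quartiles.** These do not separate the two versions. At 50% the chance of stopping at 5 is exactly one half, so the exact median is a tie between 5 and 10; the printed 10 is compatible with both. The remaining printed medians and quartiles agree with both.

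**The case against.** The best defence is that the table reports early termination. The worked example uses that word, and a crossing at 35 of a maximum of 36 patients spares at most one patient, so leaving it out would be a reasonable convention. This may be what was done. But the column is headed only Pr(stop), the section introduces the table as describing the stopping rule, and 15/35 is listed as a boundary that ends the trial. The convention is possible but undocumented. Equally, the documents do not support a reader who infers that the look at 35 was dropped by mistake: its absence from the simulation is itself inferred from the fit.

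A second defence is that two percentage points do not matter. In practice that is largely right. The large z values reflect 10,000 repetitions, not importance. Mean patients evaluated changes by at most 0.02 (19.64 against 19.66 at 40%; 12.06 against 12.08 at 50%), and no decision in the plan is taken from the table. It does not make the figures correct, because the yardstick for a simulation of an exactly computable rule is its own standard error.

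A reader might also conclude that the whole column is wrong. It is not. The 10%, 20% and 30% rows are within 1.6 standard errors of both versions, and the 30% row is slightly closer to seven looks.

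**Conclusion.** The point holds for the 40%, 50% and 60% rows and for the 90.8% example. Against the rule as written they are too low by 2.4, 2.0 and 0.4 percentage points. At a true rate of 50% the chance of not stopping is printed as 1 − 0.908 = 9.2% and is 1 − 0.928 = 7.2%.

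The calculation takes the toxicity rule alone, without the first-stage futility stop, and assumes independent patients with a common toxicity rate. The match to looks to 30 supports the same set-up in the plan's simulation.

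Two stronger readings should be resisted. The boundaries are not in error: all seven follow from the criterion, and 15/35 stands. Nor should the discrepancy be called an error on the safe side without qualification. The written rule does stop more often than the table says, but monitoring is set against 0.33 while Section 1.0 places excessive toxicity above 50%. At 40%, where the gap is largest, the two sections differ on whether toxicity is excessive.

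This is a minor reporting error, established with high confidence; its cause is an inference.

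**What to change.** One of two changes in Section 10.0, depending on what was intended:

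- Replace the Pr(stop) column with the exact seven-look values 0.0095, 0.081, 0.304, 0.670, 0.928 and 0.995, and change 90.8% to 92.8% in the example.
- If a crossing at 35 of 36 patients was deliberately not counted as early, keep the column and the example, and add a footnote that they cover the looks at 5 to 30 only.

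Neither option changes a boundary or the conduct of the trial. The editing cost is one column and one percentage, or one footnote. Section 11.0 requires agreement of the principal investigator, the institution and both supporting companies for any amendment, and adds: "Written verification of IRB approval will be obtained before any amendment is implemented". The correction therefore need not prompt an amendment of its own and can go into the next one made for another reason.

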4.0 Treatment Plan

The administration of ofatumumab will be four weekly IV infusions at the dose of 300mg week 1, 1,000 mg week 2, 3 and 4, then monthly during months 2-6 and once every two months during months 7-24 (even months: 8,10,12 etc.). Lenalidomide will be given at the dose of 10mg daily. Lenalidomide will be started on day 9 – the day after the second infusion of ofatumumab and will be continued daily. Treatment duration will be 24 cycles and it will be possible to continue lenalidomide beyond 24 cycles if there is a significant benefit such as an ongoing PR or CR. Response will be evaluated after three, six, twelve, eighteen and twenty-four cycles. Only enough lenalidomide for 28 days of therapy will be supplied to the patient each cycle. Each cycle consists of 28 days. Patients with baseline creatinine clearance or calculated GFR ≥ 30 ml/min but < 50 ml/min will begin treatment at Dose Level – 1 (lenalidomide 5mg daily). These patients may be escalated to lenalidomide 10mg daily on Day 29 or later at physician discretion based on tolerability. Dose reduction steps will follow in accordance with Table 4 taken from their current dose.

Drug Dispensing Requirements

Lenalidomide:

Lenalidomide (Revlimid®) will be provided to research subjects for the duration of their participation in this trial at no charge to them or their insurance providers. Lenalidomide will be provided in accordance with the RevAssist® program of Celgene Corporation. Per standard RevAssist® requirements all physicians who prescribe lenalidomide for research subjects enrolled into this trial, and all research subjects enrolled into this trial, must be registered in and must comply with all requirements of the RevAssist® program. Prescriptions must be filled within 7 days. Only enough lenalidomide for one cycle of therapy will be supplied to the patient each cycle.

Lenalidomide capsules should be swallowed whole, and should not be broken, chewed or opened.

If a dose of lenalidomide is missed, it should be taken as soon as possible on the same day. If it is missed for the entire day, it should not be made up.

Patients who take more than the prescribed dose of lenalidomide should be instructed to seek emergency medical care if needed and contact study staff immediately.

Labeling and Lenalidomide Distribution

Lenalidomide will be shipped directly to patients via a specialty, Registered Pharmacy. Bottles will contain a sufficient number of capsules for one cycle of dosing.

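### Read literally, the toxicity boundaries are first checked at completion of cycle 6, so the operating-characteristics table counts patients evaluated and understates patients exposed by an amount that depends on accrual

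*Combined protocol and SAP*

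**What the plan says.** Section 10.0 monitors grade 3-4 non-hematological toxicity with a beta-binomial model, "assuming a priori probability of toxicity following Beta (1,1"). The trial stops if the posterior probability that the toxicity rate exceeds 0.33 is above 0.85. The resulting boundaries, as toxicities over patients evaluated, are "3/5, 5/10, 7/15, 9/20, 11/25, 13/30" and 15/35. A table gives the stopping probability and the median number of patients with quartiles. At a true rate of 50% these are 0.908 and 10 (5, 15); at 60%, 0.991 and 5 (5, 10).

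On timing, the same section says "The first time point to evaluate efficacy and toxicity will be at completion of cycle 6 of treatment", and then "Toxicity will be monitored closely during the entire treatment, but toxicities occurring after cycle 6 will not be applied to the stopping boundaries". Section 4.0 fixes the cycle length: "Each cycle consists of 28 days".

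The only accrual pause is for efficacy. If there are 3 or fewer responses among the first 19 patients, accrual waits for a fourth responder. Nothing pauses accrual while a cohort is followed for toxicity, and the text supplied for review gives no accrual rate.

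**The concern.** A toxicity stopping rule exists to limit how many patients receive a combination that proves too toxic. If the first check waits until five patients have finished six cycles and enrolment continues meanwhile, the number treated at that check exceeds five. The table's medians of 5 and 10 would then describe the patients whose outcomes are in hand. A reader of the column, an IRB member for instance, would naturally take them as the number treated.

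The wait also buys no information once the count is reached. A counted event does not reverse, so when three of the first five patients have had one, the 3/5 boundary is bound to be met, provided all five stay in the count. The plan does not say whether it may then be acted on, or how a patient who leaves before completing cycle 6 is counted.

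**Working it through.** **1. Boundaries.** With r events in n patients the posterior is Beta(1+r, 1+n-r). The boundary is the smallest r with Pr(rate > 0.33) > 0.85. At n = 5, r = 2 gives 0.687 and r = 3 gives 0.903, so the boundary is 3. All seven listed boundaries reproduce.

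**2. The plan's table.** I used an exact binomial recursion over the looks, with each cohort's outcome known before the next cohort enters (no delay).

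| True rate | Plan Pr(stop) | Six looks, 5 to 30 | Seven looks, 5 to 35 |
|---|---|---|---|
| 0.10 | 0.011 | 0.0095 | 0.0095 |
| 0.20 | 0.084 | 0.081 | 0.081 |
| 0.30 | 0.305 | 0.298 | 0.304 |
| 0.40 | 0.646 | 0.646 | 0.670 |
| 0.50 | 0.908 | 0.908 | 0.928 |
| 0.60 | 0.991 | 0.991 | 0.995 |

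The six-look version fits the table, and every median and quartile matches, so the table appears not to count the 15/35 look. For example, Pr(3 or more of 5) is 0.683 at a true rate of 60%, which makes the median 5. Agreement with a no-delay calculation shows that the patient column counts patients evaluated.

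**3. Delay.** 6 x 28 = 168 days; 168 / 30.44 = 5.52 months.

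**4. Patients started when the fifth completes cycle 6.** Formula: 5 + floor(5.52 x monthly accrual). The accrual rates are assumptions.

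- 0.25 per month: 5 + 1 = 6
- 0.5 per month: 5 + 2 = 7
- 1 per month: 5 + 5 = 10
- 2 per month: 5 + 11 = 16
- 3 per month: 5 + 16 = 21, or 19 if the stage-1 hold is in force

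**5. Comparison with the table over all trials.** At a true rate of 50% the table's median is 10. Simulating random (Poisson) accrual with six looks, no hold and the literal wait, the median enrolled by the end of toxicity monitoring (36 if the rule never fires) is about 10, 11, 14 and 19 at 0.25, 0.5, 1 and 2 per month. At 3 and 4 per month it is 26 and 31, or 19 if the hold lasts until all 19 complete cycle 6. These medians are sensitive, because half the trials stop at the first look when the true rate is 50%.

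**6. Effect of acting when the count is reached.** I simulated steady accrual with all seven looks, the hold at 19 and event times from front-loaded to uniform over six cycles. In trials that stop:

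- At 0.25-0.5 per month, median exposure falls by 0-2 patients.
- At 2 per month and a true rate of 60%, it falls from 16 to about 8-11.
- At 2 per month and a true rate of 50%, it falls from 16 to about 10-13.

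Pr(stop) is the same under both rules (about 0.93 at 50% and 0.995 at 60%, with seven looks), because the same trials stop, only sooner. These medians cover stopped trials only, so they are not directly comparable with the table, which includes trials that run to 36.

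**The case against.** The strongest reply is that the two timing sentences together set a counting window (events in cycles 1-6) and a latest evaluation time, not a ban on acting sooner. The section also says the trial will be terminated if the ratio reaches the boundary, and three events among five patients are visible when the third occurs. This stands in part. A reader might infer that the rule cannot act before cycle 6; the documents do not say so. Nor do they say that it may, and the stated first evaluation is at completion of cycle 6. On the lenient reading, 5.5 months is the latest time for the fifth patient, not the certain one.

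A reader might also infer that many more patients, or most of stage 1, will be exposed at the first look. That needs an accrual rate the supplied text does not give. At 0.25-0.5 per month the excess is 1 or 2 patients, and at 1 per month it is 10 of 19. The cap of 19 is not fixed either: the hold lifts at the fourth responder, and response is first assessed after cycle 3 (sections 4.0 and 8.0).

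A third inference is that patients who leave early for toxicity drop out of the count. No text excludes them, and section 4.0 requires lenalidomide to be discontinued for several severe toxicities, so excluding such patients would defeat the rule. What remains is that the plan is silent on them.

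Finally, serious adverse events go to the companies within 24 hours (section 9.0), and the investigator and both companies may discontinue the study for medical reasons (section 11.0). These safeguards temper the consequence, but neither triggers the boundary.

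**Conclusion.** The concern holds in a limited form. On the literal reading, the 3/5 look comes about 5.5 months after the fifth patient starts, with no accrual pause for toxicity, and the table makes no allowance for that lag. The table therefore understates exposure whenever accrual exceeds about one patient per 5.5 months. The excess at the first look ranges from 1 patient at 0.25 per month to 11 at 2 per month. The benefit of acting earlier is likewise small under slow accrual and several patients at 2 per month.

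All exposure figures rest on assumed steady or Poisson accrual, and the savings rest also on assumed event timing. The unchanged stopping probabilities, and the certainty that three events in the first five will meet the boundary, both require early leavers to be counted. Even on the lenient reading the change is worth making, because it replaces the stated evaluation time with one that exposes no more patients and often fewer.

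**What to change.** In section 10.0:

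- State that the boundaries apply to the first 5, 10, 15, ... patients who start treatment, including those who leave before completing cycle 6.
- State that a boundary is acted on as soon as the number of grade 3-4 non-hematological events in cycles 1-6 in that group reaches it, without waiting for the others to complete cycle 6.
- Label the table's patient column as patients evaluated (no delay).

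Giving the expected accrual rate beside the table would let readers judge exposure.

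The cost is two sentences and a column label. No patients are added and, with early leavers counted, the stopping probabilities are unchanged. The small downside is that qualifying events must be tallied as they occur, which the close monitoring already promised should supply.
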